14.3 Safety Data

14.3.1 Displays of Adverse Events

14.3.1.1 Solicited Adverse Events

Table 35: Number and Percentage of Subjects Experiencing Solicited Events with 95% Confidence Intervals by Symptom and Treatment Group, - Asymptomatic Amebiasis Group

Symptom	Auranofin, 6 mg (N=X)			Placebo (N=X)		
	n	%	95% CI	n	%	95% CI
Any Symptom	x	x.x	x.x, x.x	x	x.x	x.x, x.x
Loose stools or diarrhea						
Abdominal Pain						
Nausea with or without vomiting						
Constipation						
Anorexia						
Flatulence						
Dyspepsia						
Dysgeusia						

Table 35: Number and Percentage of Subjects Experiencing Solicited Events With 95% Confidence Intervals by Symptom and Treatment Group, - Asymptotic Amebiasis Group (continued)

Symptom	Auranofin, 6 mg (N=X)			Placebo (N=X)		
	n	%	95% CI	n	%	95% CI
Pruritus						
Hair loss						
Urticaria						
Stomatitis						
Conjunctivitis						
Glossitis						
Hematuria						
Rash						

Table will be repeated for the symptomatic study population but will exclude loose stools or diarrhea.

Table 36: Number and Percentage of Subjects Experiencing Solicited Events with 95% Confidence Intervals by Symptom and Treatment Group, Asymptomatic Giardiasis Group

Symptom	Auranofin, 6 mg (N=X)			Placebo (N=X)		
	n	%	95% CI	n	%	95% CI
Any Symptom	x	x.x	x.x, x.x	x	x.x	x.x, x.x
Loose stools or diarrhea						
Abdominal Pain						
Nausea with or without vomiting						
Constipation						
Anorexia						
Flatulence						
Dyspepsia						
Dysgeusia						
Pruritus						
Hair loss						
Urticaria						

Table 36: Number and Percentage of Subjects Experiencing Solicited Events with 95% Confidence Intervals by Symptom and Treatment Group, Asymptomatic Giardiasis Group

Symptom	Auranofin, 6 mg (N=X)			Placebo (N=X)		
	n	%	95% CI	n	%	95% CI
Stomatitis						
Conjunctivitis						
Glossitis						
Hematuria						
Rash						

N = Number of subjects in the Safety Analysis Population who received the specified dose. Severity is the maximum severity reported.

Table will be repeated for the symptomatic study population but will exclude loose stools or diarrhea.

14.3.1.2 Unsolicited Adverse Events**Table 37: Number and Percentage of Subjects Experiencing Unsolicited Adverse Events by MedDRA System Organ Class and Preferred Term, Maximum Severity, Relationship, Asymptomatic Amebiasis Group, Auranofin, 6 mg (n=x)**

MedDRA System Organ Class	MedDRA Preferred Term	Any Incidence		Severity [1]				Relationship to Treatment [2]			
				Mild		Moderate		Severe		Not Related	
		n	%	n	%	n	%	n	%	n	%
Any SOC	Any PT	x	x.x	x	x.x	x	x.x	x	x.x	x	x.x
[SOC 1]	Any PT										
	[PT 1]										
	[PT 2]										
[SOC 2]	Any PT										
	[PT 1]										
	[PT 2]										

Note: N = Number of subjects in the Safety Analysis Population.

[1] For severity, a subject is counted once per preferred term and is summarized according to their highest severity.

[2] For relationship, a subject is only counted once per preferred term and is summarized according to their closest relationship.

Table will be repeated for the symptomatic study population.

Table 38: Number and Percentage of Subjects Experiencing Unsolicited Adverse Events by MedDRA System Organ Class and Preferred Term, Maximum Severity, Relationship, Asymptomatic Amebiasis Group, Placebo (n=x)

MedDRA System Organ Class	MedDRA Preferred Term	Any Incidence		Severity [1]				Relationship to Treatment [2]			
				Mild		Moderate		Severe		Not Related	
		n	%	n	%	n	%	n	%	n	%
Any SOC	Any PT	x	x.x	x	x.x	x	x.x	x	x.x	x	x.x
[SOC 1]	Any PT										
	[PT 1]										
	[PT 2]										
[SOC 2]	Any PT										
	[PT 1]										
	[PT 2]										

Note: N = Number of subjects in the Safety Analysis Population.

[1] For severity, a subject is counted once per preferred term and is summarized according to their highest severity.

[2] For relationship, a subject is only counted once per preferred term and is summarized according to their closest relationship.

Table will be repeated for the symptomatic study population.

Table 39: Number and Percentage of Subjects Experiencing Unsolicited Adverse Events by MedDRA System Organ Class and Preferred Term, Maximum Severity, Relationship, Asymptomatic Giardiasis Group, Auranofin, 6 mg (n=x)

MedDRA System Organ Class	MedDRA Preferred Term	Any Incidence		Severity [1]				Relationship to Treatment [2]			
				Mild		Moderate		Severe		Not Related	
		n	%	n	%	n	%	n	%	n	%
Any SOC	Any PT	x	x.x	x	x.x	x	x.x	x	x.x	x	x.x
[SOC 1]	Any PT										
	[PT 1]										
	[PT 2]										
[SOC 2]	Any PT										
	[PT 1]										
	[PT 2]										

Note: N = Number of subjects in the Safety Analysis Population.

[1] For severity, a subject is counted once per preferred term and is summarized according to their highest severity.

[2] For relationship, a subject is only counted once per preferred term and is summarized according to their closest relationship.

Table will be repeated for the symptomatic study population.

Table 40: Number and Percentage of Subjects Experiencing Unsolicited Adverse Events by MedDRA System Organ Class and Preferred Term, Maximum Severity, Relationship, Asymptomatic Giardiasis Group, Placebo (n=x)

MedDRA System Organ Class	MedDRA Preferred Term	Any Incidence		Severity [1]				Relationship to Treatment [2]			
				Mild		Moderate		Severe		Not Related	
		n	%	n	%	n	%	n	%	n	%
Any SOC	Any PT	x	x.x	x	x.x	x	x.x	x	x.x	x	x.x
[SOC 1]	Any PT										
	[PT 1]										
	[PT 2]										
[SOC 2]	Any PT										
	[PT 1]										
	[PT 2]										

Note: N = Number of subjects in the Safety Analysis Population.

[1] For severity, a subject is counted once per preferred term and is summarized according to their highest severity.

[2] For relationship, a subject is only counted once per preferred term and is summarized according to their closest relationship.

Table will be repeated for the symptomatic study population.

14.3.2 Listing of Deaths, Other Serious and Significant Adverse Events**Table 41: Listing of Serious Adverse Events***Listings will be sorted by study population, disease group, treatment group, subject ID*

Adverse Event	Associated with Dose No.	No. of Days Post Associated Dose (Duration)	No. of Days Post Dose the Event Became Serious	Reason Reported as an SAE	Severity	Relationship to Study Treatment	If Not Related, Alternative Etiology	Action Taken with Study Treatment	Subject Discontinued Due to AE	Outcome	MedDRA System Organ Class	MedDRA Preferred Term
Subject ID: , Study Population: , Disease Group: , Treatment Group: , AE Number:												
Comments:												
Subject ID: , Study Population: , Disease Group: , Treatment Group: , AE Number:												
Comments:												

Table 42: Listing of Non-Serious, Unsolicited, Moderate or Severe Adverse Events, Asymptomatic Amebiasis Group*Table will be repeated for the symptomatic population.*

Adverse Event	Associated with Dose No.	No. of Days Post Associated Dose (Duration)	Severity	Relationship to Study Treatment	If Not Related, Alternative Etiology	Action Taken with Study Treatment	Subject Discontinued Due to AE	Outcome	MedDRA System Organ Class	MedDRA Preferred Term
Subject ID: , Treatment Group: , AE Number:										
Comments:										
Subject ID: , Treatment Group: , AE Number:										
Comments:										

Table 43: Listing of Non-Serious, Unsolicited, Moderate or Severe Adverse Events, Asymptomatic Giardiasis Group*Table will be repeated for the symptomatic population.*

Adverse Event	Associated with Dose No.	No. of Days Post Associated Dose (Duration)	Severity	Relationship to Study Treatment	If Not Related, Alternative Etiology	Action Taken with Study Treatment	Subject Discontinued Due to AE	Outcome	MedDRA System Organ Class	MedDRA Preferred Term
Subject ID: , Treatment Group: , AE Number:										
Comments:										
Subject ID: , Treatment Group: , AE Number:										
Comments:										

14.3.3 Narratives of Deaths, Other Serious and Significant Adverse Events

(not included in SAP, but this is a placeholder for the CSR)

[This section of the clinical study report will include narrative text of deaths, serious, and significant adverse events.]

14.3.4 Abnormal Laboratory Value Listings (by Subject)**Table 44: Listing of Abnormal Laboratory Results, Asymptomatic Amebiasis Group**

Subject ID	Treatment Group	Sex	Age (years)	Planned Time Point	Actual Study Day	Laboratory Parameter (Units)	Result (Severity)	Relationship to Treatment	If Not Related, Alternate Etiology	Action Taken with Study Treatment	Subject Discontinued Due to Result?

Table 45: Listing of Abnormal Laboratory Results, Asymptomatic Giardiasis Group

Subject ID	Treatment Group	Sex	Age (years)	Planned Time Point	Actual Study Day	Laboratory Parameter (Units)	Result (Severity)	Relationship to Treatment	If Not Related, Alternate Etiology	Action Taken with Study Treatment	Subject Discontinued Due to Result?

Repeat for symptomatic study population.

14.3.5 Displays of Laboratory Results

Table 46: Laboratory Results by Parameter, Maximum Severity, Study Day, and Treatment Group, Asymptomatic Amebiasis Group - Any Laboratory Parameter

Any laboratory parameter	Treatment Group	N	None		Mild/Grade 1 (Low)		Mild/Grade 1 (High)		Moderate/Grade 2 (Low)		Moderate/Grade 2 (High)		Severe/Grade 3 (Low)		Severe/Grade 3 (High)		Missing	
			n	%	n	%	n	%	n	%	n	%	n	%	n	%	n	%
Baseline	Auranofin, 6 mg	x	x	x.x	x	x.x	x	x.x	x	x.x	x	x.x	x	x.x	x	x.x	x	x.x
	Placebo																	
Day 7	Auranofin, 6 mg																	
	Placebo																	

Repeat for symptomatic study population.

Table 47: Laboratory Results by Parameter, Maximum Severity, Study Day, and Treatment Group, Asymptomatic Amebiasis Group - White Blood Cell Count

White Blood Cell Count	Treatment Group	N	None		Mild/Grade 1 (Low)		Mild/Grade 1 (High)		Moderate/Grade 2 (Low)		Moderate/Grade 2 (High)		Severe/Grade 3 (Low)		Severe/Grade 3 (High)		Missing	
			n	%	n	%	n	%	n	%	n	%	n	%	n	%	n	%
Baseline	Auranofin, 6 mg	x	x	x.x	x	x.x	x	x.x	x	x.x	x	x.x	x	x.x	x	x.x	x	x.x
	Placebo																	
Day 7	Auranofin, 6 mg																	
	Placebo																	

Repeat for symptomatic study population.

Table 48: Laboratory Results by Parameter, Maximum Severity, Study Day, and Treatment Group, Asymptomatic Amebiasis Group - Hemoglobin

Hemoglobin	Treatment Group	N	None		Mild/ Grade 1		Moderate/ Grade 2		Severe/ Grade 3		Missing	
			n	%	n	%	n	%	n	%	n	%
Baseline	Auranofin, 6 mg	x	x	x.x	x	x.x	x	x.x	x	x.x	x	x.x
	Placebo											
Day 7	Auranofin, 6 mg											
	Placebo											

*Repeat for symptomatic study population.***Table 49: Laboratory Results by Parameter, Maximum Severity, Study Day, and Treatment Group, Asymptomatic Amebiasis Group - Hematocrit**

Hematocrit	Treatment Group	N	None		Mild/ Grade 1		Moderate/ Grade 2		Severe/ Grade 3		Missing	
			n	%	n	%	n	%	n	%	n	%
Baseline	Auranofin, 6 mg	x	x	x.x	x	x.x	x	x.x	x	x.x	x	x.x
	Placebo											
Day 7	Auranofin, 6 mg											
	Placebo											

Repeat for symptomatic study population.

Table 50: Laboratory Results by Parameter, Maximum Severity, Study Day, and Treatment Group, Asymptomatic Amebiasis Group - Platelets

Platelets	Treatment Group	N	None		Mild/ Grade 1 (Low)		Mild/ Grade 1 (High)		Moderate/ Grade 2 (Low)		Moderate/ Grade 2 (High)		Severe/ Grade 3 (Low)		Severe/ Grade 3 (High)		Missing	
			n	%	n	%	n	%	n	%	n	%	n	%	n	%	n	%
Baseline	Auranofin, 6 mg	x	x	x.x	x	x.x	x	x.x	x	x.x	x	x.x	x	x.x	x	x.x	x	x.x
	Placebo																	
Day 7	Auranofin, 6 mg																	
	Placebo																	

Repeat for symptomatic study population.

Table 51: Abnormal Laboratory Results Related to Study Treatment by Parameter, Maximum Severity, Study Day, and Treatment Group, Asymptomatic Amebiasis Group -White Blood Cell Count

White Blood Cell Count	Treatment Group	N	Mild/ Grade 1 (Low)		Mild/ Grade 1 (High)		Moderate/ Grade 2 (Low)		Moderate/ Grade 2 (High)		Severe/ Grade 3 (Low)		Severe/ Grade 3 (High)		Missing	
			n	%	n	%	n	%	n	%	n	%	n	%	n	%
Baseline	Auranofin, 6 mg	x	x	x.x	x	x.x	x	x.x	x	x.x	x	x.x	x	x.x	x	x.x
	Placebo															
Day 7	Auranofin, 6 mg															
	Placebo															

Repeat for symptomatic study population.

Table 52: Abnormal Laboratory Results Related to Study Treatment by Parameter, Maximum Severity, Study Day, and Treatment Group, Asymptomatic Amebiasis Group - Hemoglobin

Hemoglobin	Treatment Group	N	Mild/ Grade 1		Moderate/ Grade 2		Severe/ Grade 3		Missing	
			n	%	n	%	n	%	n	%
Baseline	Auranofin, 6 mg	x	x	x.x	x	x.x	x	x.x	x	x.x
	Placebo									
Day 7	Auranofin, 6 mg									

Repeat for symptomatic study population.

Table 53: Abnormal Laboratory Results Related to Study Treatment by Parameter, Maximum Severity, Study Day, and Treatment Group, Asymptomatic Amebiasis Group - Hematocrit

Hematocrit	Treatment Group	N	Mild/ Grade 1		Moderate/ Grade 2		Severe/ Grade 3		Missing	
			n	%	n	%	n	%	n	%
Baseline	Auranofin, 6 mg	x	x	x.x	x	x.x	x	x.x	x	x.x
	Placebo									
Day 7	Auranofin, 6 mg									
	Placebo									

*Repeat for symptomatic study population.***Table 54: Abnormal Laboratory Results Related to Study Treatment by Parameter, Maximum Severity, Study Day, and Treatment Group, Asymptomatic Amebiasis Group - Platelets**

Platelets	Treatment Group	N	Mild/ Grade 1 (Low)		Mild/ Grade 1 (High)		Moderate/ Grade 2 (Low)		Moderate/ Grade 2 (High)		Severe/ Grade 3 (Low)		Severe/ Grade 3 (High)		Missing	
			n	%	n	%	n	%	n	%	n	%	n	%	n	%
Baseline	Auranofin, 6 mg	x	x	x.x	x	x.x	x	x.x	x	x.x	x	x.x	x	x.x	x	x.x
	Placebo															
Day 7	Auranofin, 6 mg															
	Placebo															

Repeat for symptomatic study population

Table 55: Abnormal Laboratory Results Related to Study Treatment by Parameter, Maximum Severity, Study Day, and Treatment Group, Asymptomatic Giardiasis Group -White Blood Cell Count

White Blood Cell Count	Treatment Group	N	Mild/Grade 1 (Low)		Mild/Grade 1 (High)		Moderate/Grade 2 (Low)		Moderate/Grade 2 (High)		Severe/Grade 3 (Low)		Severe/Grade 3 (High)		Missing	
			n	%	n	%	n	%	n	%	n	%	n	%	n	%
Baseline	Auranofin, 6 mg	x	x	x.x	x	x.x	x	x.x	x	x.x	x	x.x	x	x.x	x	x.x
	Placebo															
Day 7	Auranofin, 6 mg															
	Placebo															

*Repeat for symptomatic study population.***Table 56: Abnormal Laboratory Results Related to Study Treatment by Parameter, Maximum Severity, Study Day, and Treatment Group, Asymptomatic Giardiasis Group - Hemoglobin**

Hemoglobin	Treatment Group	N	Mild/Grade 1		Moderate/Grade 2		Severe/Grade 3		Missing	
			n	%	n	%	n	%	n	%
Baseline	Auranofin, 6 mg	x	x	x.x	x	x.x	x	x.x	x	x.x
	Placebo									
Day 7	Auranofin, 6 mg									
	Placebo									

Repeat for symptomatic study population.

Table 57: Abnormal Laboratory Results Related to Study Treatment by Parameter, Maximum Severity, Study Day, and Treatment Group, Asymptomatic Giardiasis Group - Hematocrit

Hematocrit	Treatment Group	N	Mild/ Grade 1		Moderate/ Grade 2		Severe/ Grade 3		Missing	
			n	%	n	%	n	%	n	%
Baseline	Auranofin, 6 mg	x	x	x.x	x	x.x	x	x.x	x	x.x
	Placebo									
Day 7	Auranofin, 6 mg									
	Placebo									

*Repeat for symptomatic study population.***Table 58: Abnormal Laboratory Results Related to Study Treatment by Parameter, Maximum Severity, Study Day, and Treatment Group, Asymptomatic Giardiasis Group - Platelets**

Platelets	Treatment Group	N	Mild/ Grade 1 (Low)		Mild/ Grade 1 (High)		Moderate/ Grade 2 (Low)		Moderate/ Grade 2 (High)		Severe/ Grade 3 (Low)		Severe/ Grade 3 (High)		Missing	
			n	%	n	%	n	%	n	%	n	%	n	%	n	%
Baseline	Auranofin, 6 mg	x	x	x.x	x	x.x	x	x.x	x	x.x	x	x.x	x	x.x	x	x.x
	Placebo															
Day 7	Auranofin, 6 mg															
	Placebo															

Repeat for symptomatic study population.

Table 59: Laboratory Summary Statistics by Parameter, Study Day, and Treatment Group, Asymptomatic Amebiasis Group - White Blood Cells

Time Point	Treatment Group	N	Mean	Standard Deviation	Median	Min, Max
Baseline	Auranofin, 6 mg	x	xx.xx	xx.xx	xx.x	xx.x, xx.x
	Placebo					
Day 7	Auranofin, 6 mg					
	Placebo					
Day 7, Change from Baseline	Auranofin, 6 mg					
	Placebo					

N = Number of subjects in the Safety population with non-missing values for the parameter of interest.

*Repeat for symptomatic study population.***Table 60: Laboratory Summary Statistics by Parameter, Study Day, and Treatment Group, Asymptomatic Amebiasis Group - Hemoglobin**

Time Point	Treatment Group	N	Mean	Standard Deviation	Median	Min, Max
Baseline	Auranofin, 6 mg	x	xx.xx	xx.xx	xx.x	xx.x, xx.x
	Placebo					
Day 7	Auranofin, 6 mg					
	Placebo					
Day 7, Change from Baseline	Auranofin, 6 mg					
	Placebo					

N = Number of subjects in the Safety population with non-missing values for the parameter of interest.

Repeat for symptomatic study population.

Table 61: Laboratory Summary Statistics by Parameter, Study Day, and Treatment Group, Asymptomatic Amebiasis Group -Hematocrit

Time Point	Treatment Group	N	Mean	Standard Deviation	Median	Min, Max
Baseline	Auranofin, 6 mg	x	xx.x	xx.x	x	xx, xx
	Placebo					
Day 7	Auranofin, 6 mg					
	Placebo					
Day 7, Change from Baseline	Auranofin, 6 mg					
	Placebo					

N = Number of subjects in the Safety population with non-missing values for the parameter of interest.

*Repeat for symptomatic study population.***Table 62: Laboratory Summary Statistics by Parameter, Study Day, and Treatment Group, Asymptomatic Amebiasis Group - Platelets**

Time Point	Treatment Group	N	Mean	Standard Deviation	Median	Min, Max
Baseline	Auranofin, 6 mg	x	xx.xx	xx.xx	xx.x	xx.x, xx.x
	Placebo					
Day 7	Auranofin, 6 mg					
	Placebo					
Day 7, Change from Baseline	Auranofin, 6 mg					
	Placebo					

N = Number of subjects in the Safety population with non-missing values for the parameter of interest.

Repeat for symptomatic study population.

Table 63: Laboratory Summary Statistics by Parameter, Study Day, and Treatment Group, Asymptomatic Giardiasis Group - White Blood Cells

Time Point	Treatment Group	N	Mean	Standard Deviation	Median	Min, Max
Baseline	Auranofin, 6 mg	x	xx.xx	xx.xx	xx.x	xx.x, xx.x
	Placebo					
Day 7	Auranofin, 6 mg					
	Placebo					
Day 7, Change from Baseline	Auranofin, 6 mg					
	Placebo					

N = Number of subjects in the Safety population with non-missing values for the parameter of interest.

*Repeat for symptomatic study population.***Table 64: Laboratory Summary Statistics by Parameter, Study Day, and Treatment Group, Asymptomatic Giardiasis Group - Hemoglobin**

Time Point	Treatment Group	N	Mean	Standard Deviation	Median	Min, Max
Baseline	Auranofin, 6 mg	x	xx.xx	xx.xx	xx.x	xx.x, xx.x
	Placebo					
Day 7	Auranofin, 6 mg					
	Placebo					
Day 7, Change from Baseline	Auranofin, 6 mg					
	Placebo					

N = Number of subjects in the Safety population with non-missing values for the parameter of interest.

Repeat for symptomatic study population.

Table 65: Laboratory Summary Statistics by Parameter, Study Day, and Treatment Group, Asymptomatic Giardiasis Group - Hematocrit

Time Point	Treatment Group	N	Mean	Standard Deviation	Median	Min, Max
Baseline	Auranofin, 6 mg	x	xx.x	xx.x	x	xx, xx
	Placebo					
Day 7	Auranofin, 6 mg					
	Placebo					
Day 7, Change from Baseline	Auranofin, 6 mg					
	Placebo					

N = Number of subjects in the Safety population with non-missing values for the parameter of interest.

*Repeat for symptomatic study population.***Table 66: Laboratory Summary Statistics by Parameter, Study Day, and Treatment Group, Asymptomatic Giardiasis Group - Platelets**

Time Point	Treatment Group	N	Mean	Standard Deviation	Median	Min, Max
Baseline	Auranofin, 6 mg	x	xx.xx	xx.xx	xx.x	xx.x, xx.x
	Placebo					
Day 7	Auranofin, 6 mg					
	Placebo					
Day 7, Change from Baseline	Auranofin, 6 mg					
	Placebo					

N = Number of subjects in the Safety population with non-missing values for the parameter of interest.

Repeat for symptomatic study population.

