9.2 Methods and Timing for Assessing, Recording, and Analyzing Safety Parameters

9.2.1 Adverse Events

Adverse Event: International Conference on Harmonisation (ICH) E6 defines an AE as any untoward medical occurrence in a patient or clinical investigation subject administered a pharmaceutical product regardless of its causal relationship to the study treatment. An AE can therefore be any unfavorable and unintended sign (including an abnormal laboratory finding), symptom, or disease temporally associated with the use of a medicinal (investigational) product. The occurrence of an AE may come to the attention of study personnel during study visits and interviews of a study recipient presenting for medical care, or upon review by a study monitor.

AEs not meeting the protocol-defined criteria for SAEs will be captured on the appropriate data collection form and electronic case report form (eCRF). Information to be collected for unsolicited AEs includes event description, date of onset, licensed clinician's assessment of severity and relationship to study product and alternate etiology (if not related to study product) (assessed only by those with the training and authority to make a diagnosis and listed on the Form FDA 1572 as the site principal investigator or sub-investigator), date of resolution of the event, seriousness and outcome. AEs while on study will be documented appropriately regardless of relationship. AEs will be followed to resolution.

Any medical condition that is present at the time that the subject is screened will be considered as baseline and not reported as an AE. However, if the severity of any pre-existing medical condition increases, it will be recorded as an AE.

AEs must be graded for severity and assessed for relationship to study product (see definitions below). Adverse events characterized as intermittent require documentation of onset and duration of each episode. The start and stop date of each reported AE will be recorded on the appropriate data collection form and eCRF.

FDA defines an AE as any untoward medical occurrence associated with the use of a drug in humans, whether or not considered drug related.

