³The normal ranges for Icddr,b laboratory tests include (a) blood urea nitrogen (BUN) between 5 and 24 mg/dL, inclusive, (b) creatinine between 53 and 106 umol/L, inclusive, males and between 44 and 97umol/L, inclusive, for females, (c) AST of 38 U/L or less for males and 32 U/L or less for females (d) ALT of 41.0 U/L or less for males and 31 U/L or less for females, (e) WBC between 4.0 and 11.0 10⁹/L, inclusive (f) platelets between 150 and 450 10⁹/L, inclusive, (g) hemoglobin between 12.5 and 17.5 gm/dL, inclusive, for males and 11.5 and 16.5 gm/dL, inclusive, for females,

Subjects will be eligible for enrollment with the following laboratory values:

- Blood urea nitrogen less than 30 mg/dL
- Creatinine less than 133 umol/L
- AST or ALT less than 60.0 U/L
- White cell count between 3.5 and 11.0 (10⁹/L)
- Platelets between 100 and 500 (10⁹/L)
- Hemoglobin between 11.0 and 18.0 gm/dL

8. Urinalysis with no greater than trace protein. If a high protein is confirmed to be due to menstruation, it should be repeated.
9. Women of reproductive potential⁴ must have a negative urine pregnancy test within 72 hours of starting study medications.

⁴Female subjects who are surgically sterile via tubal sterilization, bilateral oophorectomy or hysterectomy or who have been postmenopausal for greater than 1 year are not considered to be of reproductive potential.

10. Female subjects participating in sexual activity that could lead to pregnancy must agree to use highly effective⁵ contraception while receiving auranofin and for 15 weeks after.

⁵Highly effective methods of contraception are defined as having low failure rates (i.e. less than 1% per year) when used consistently and correctly and may include, but are not limited to, abstinence from intercourse, monogamous relationship with a vasectomized partner, male condoms with spermicide, diaphragm with spermicide, intrauterine devices, and licensed hormonal methods. If an eligible female of child-bearing potential is not using effective contraception, hormonal contraceptives will be supplied to female subjects and condoms will be provided for her partner while they are on the trial and for the follow-up period of 4 months total. Females on effective forms of birth control will continue while on the study and for the follow-up period of 4 months total and also be provided condoms for their partners. The method and compliance of birth control used will be confirmed and documented at all study visits.

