Solicited events are AEs that are known to occur with this study product. Adverse event data is collected at each visit using specific questions and/or targeted physical examination. Based on the adverse reactions listed on the package insert, these include: loose stools or diarrhea, abdominal pain, nausea with or without vomiting, constipation, anorexia, flatulence, dyspepsia, dysgeusia, pruritus, hair loss, urticarial, stomatitis, conjunctivitis, glossitis, hematuria, and rashes. As noted above, diarrhea is considered an adverse event only in the asymptomatic population as it is a condition for enrollment in the symptomatic population. Physical examinations look for abdominal pain, hair loss, urticaria, rashes, stomatitis, conjunctivitis, and glossitis. In the symptomatic population, solicited AEs are not collected that are related to any prescribed metronidazole. Adverse event collection continues until Day 28 (following three half-lives of the drug). Each solicited adverse event described above is graded as Mild (Grade 1) if it “Does not interfere with daily activity”, as Moderate (Grade 2) if it “Interferes with daily activity”, and as Severe (Grade 3) if it “Prevents daily activity (incapacitating)”. Grading for vital signs, also collected on every visit, is given in [Table 6](#). Furthermore, hematology, biochemistry, and urine labs are analyzed on Study Day 7. Grading for these adverse events is given in [Table 7](#). Some laboratory grading ranges were modified in protocol updates; these modifications are displayed in the table. Laboratory results are graded according to the protocol effective on the date the sample was collected. The effective date is the date that the site received IRB approval for the version and began implementing that version. (The effective date is later than the protocol version date, which indicates when the version was approved by DMID.) The first subjects in the study enrolled under Protocol Version 4.0, so laboratory ranges for earlier protocol versions are not displayed. The effective dates are as follows: Version 4.0: 18Oct2016, Version 5.0: 12Dec2017, Version 6.0: 07Aug2018, Version 7.0: 23Jul2019.

Table 6: Vital Signs Grading Scale

Vital Signs*			
Vital Signs	Mild (Grade 1)	Moderate (Grade 2)	Severe (Grade 3)
Fever (°C) **	37.8-38.4	38.5-38.9	>= 39.0
Hypertension (systolic) mm Hg	141-150	151-155	>155 or an ER visit or hospitalization for malignant hypertension

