Hypertension (diastolic) mm Hg	91-95	96-100	>100 or an ER visit or hospitalization for malignant hypertension
Hypotension (systolic) mm Hg	85-89	80-84	<80 or an ER visit or hospitalization for hypotensive shock
Bradycardia – beats per minute ***	50-54 or >10 bpm less than baseline if baseline < 60	45-49 or >15 bpm less than baseline if baseline < 60	<45 or > 20 BPM or less than baseline if baseline < 60, or an ER visit or hospitalization for arrhythmia
Tachycardia – beats per minute	101-115	116-130	>130 or an ER visit or hospitalization for arrhythmia

* Subjects should be at rest for at least 15 minutes prior to vital sign measurements
 ** Oral temperature; no recent hot or cold beverages or smoking
 *** When resting heart rate is between 60-100 beats per minute. Pulse and Blood Pressure assessed at Visit 1 (Day 1) will be considered baseline. Sinus bradycardia among some healthy subject populations, for example, conditioned athletes maybe acceptable

Table 7: Laboratory Adverse Event Grading Scale

NOTE: For grading ranges that were updated in protocol revisions, all ranges are shown in the below table, with their corresponding protocol versions. No subjects were enrolled under Protocol Versions 1-3, so ranges from those versions are omitted. Events are graded according to the protocol version that was active at the time of the event. Effective dates are: Version 4.0: 18Oct2016, Version 5.0: 12Dec2017, Version 6.0: 07Aug2018, Version 7.0: 23Jul2019

Hematology	Mild (Grade 1)	Moderate (Grade 2)	Severe (Grade 3)
WBC 10 ⁹ /L (Decrease)	Version 4: 3.0-3.9 Versions 5-7: 3.0 – 3.4	2.0-2.9	<2.0
WBC 10 ⁹ /L (Increase)	Version 4: 11.1-13.0 Versions 5-7: 13.1-13.9	Version 4: 13.1-15.0 Versions 5-7: 14.0-15.0	>15.0
Hgb g/dL (Decrease) (Female)	Versions 4-6: 9-11.4 Version 7: 9.1-10.9	7.5-9.0	<7.5
Hgb g/dL (Decrease) (Male)	Versions 4-6: 9-12.4 Version 7: 9.1-10.9	7.5-9.0	<7.5
Hgb g/dL (Increase)	Versions 4-6: N/A Version 7: 18.1-18.5	Versions 4-6: N/A Version 7: 18.6-19.0	Versions 4-6: N/A Version 7: >19.0
Platelets 10 ⁹ /L (Decrease)	Version 4: 100-149 Versions 5-7: 100-130	50-99	<50
Platelets 10 ⁹ /L (Increase)	Version 4: 451-480 Versions 5-7: 551-600	Version 4: 480-500 Versions 5-7: 601-700	Version 4: >500 Versions 5-7: >700

Chemistry	Mild (Grade 1)	Moderate (Grade 2)	Severe (Grade 3)
BUN mg/dL	Version 4: 25-60 Versions 5-7: 31-60	Versions 4-7: 60-70 [†] Version 8: >60 and ≤70	>70

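### The symptomatic hemoglobin severity tables would merge low and high grades, and the asymptomatic severity tables give no by-arm count of grades that are new or worse at Day 7

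*SAP*

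**What the plan says.** SAP section 9.6 and Appendix 1, section 14.3.5, lay out the laboratory severity displays.

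- Tables 46-50 count subjects at each grade, by arm, in a Baseline row and a Day 7 row. Nothing cross-classifies the two rows, and no rule restricts Day 7 counts to new or worsened grades.
- The hemoglobin shell, "Table 48: Laboratory Results by Parameter, Maximum Severity, Study Day, and Treatment Group, Asymptomatic Amebiasis Group - Hemoglobin", has single Mild, Moderate and Severe columns and is marked for repetition in the symptomatic population. Tables 52 and 56 are built the same way. The any-parameter, white cell and platelet shells split each grade into Low and High.
- Tables 51-58 are limited to abnormal results judged related to treatment, yet each has Baseline rows.
- The numeric summaries, Tables 59-66, do carry a row "Day 7, Change from Baseline".

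The grading scale is SAP Table 7. Grade 1 low hemoglobin for women reads "Versions 4-6: 9-11.4 Version 7: 9.1-10.9"; Grade 1 high hemoglobin reads "Versions 4-6: N/A Version 7: 18.1-18.5". SAP section 4.5.1 says which version applies: "Laboratory results are graded according to the protocol effective on the date the sample was collected".

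For entry, the asymptomatic (Version 4) criteria in SAP section 4.3.1.1 include "Platelets between 100 and 500", while Table 7 gives Grade 1 low platelets as "Version 4: 100-149".

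**The concern.** There are two separate weaknesses in how the tables count.

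The first is direction. Anemia is a labelled reaction to auranofin, and a high hemoglobin is the opposite finding. A table that adds the two cannot be read as a count of either. The scale of the expected signal makes this matter. Protocol section 2.3.1 puts anemia, leucopenia and thrombocytopenia at up to 3% in long-term use. In an arm of 34 that is 0.03 × 34 = 1.02 subjects, so a single high value is as large as the signal. Exposure here is only 5 to 7 days, so the 3% serves only as a scale.

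The second is carry-over. If a subject may enter with a value that already has a grade, an unchanged value is counted at Day 7 as if it were a finding of the treatment period. Two marginal counts do not show whether the same or different subjects are affected.

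**Working it through.** No figure in the plan needs reproducing. The check sets entry limits against graded ranges, version by version, and then asks what two margins can tell.

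**1. Hemoglobin direction.** High hemoglobin has no grade in Versions 4-6. Under Version 7 it has three: 18.1-18.5, 18.6-19.0 and above 19.0. Low Grade 1 under Version 7 is 9.1-10.9. A value of 10.5 and a value of 18.3 are therefore both Mild in the repeated shell. This can happen only for samples taken from 23Jul2019 on. With 34 per arm, one high value adds 1/34 = 2.9 points.

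**2. Overlap under Version 7 (symptomatic; SAP section 4.3.2.1 against Table 7).**

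| Parameter | Eligible | Grade 1 begins | Overlap |
|---|---|---|---|
| BUN | up to 30 | 31 | none |
| Creatinine | up to 133 | 134 | none |
| AST, ALT | up to 70.0 | 70.1 | none |
| White cells | 3.5-13.0 | 3.4 or 13.1 | none |
| Platelets | 131-550 | 130 or 551 | none |
| Hemoglobin | 11.0-18.0 | 10.9 or 18.1 | none |
| Urine protein | at most trace | 1+ | none |

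An eligible Version 7 subject has no grade at entry, so every Day 7 grade is new.

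**3. Overlap under Version 4 (asymptomatic; SAP section 4.3.1.1 against Table 7).** Eligible values that already carry a grade:

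- platelets 100-149 (Grade 1) and 451-500 (Grade 1, reaching Grade 2 in 480-500)
- white cells 3.5-3.9
- hemoglobin 11.0-11.4 in women, 11.0-12.4 in men
- BUN 25 to below 30
- creatinine 98 (women) or 107 (men) to below 133
- AST 32.1 (women) or 38.1 (men) to below 60; ALT 31.1 or 41.1 to below 60

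This takes the second list in that criterion, the one worded as the eligibility rule. The laboratory normal ranges in the same item are narrower and would leave no overlap.

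**4. Versions 5-6 (symptomatic).** Low hemoglobin is still Grade 1 up to 11.4 (women) or 12.4 (men). The documents do not give the entry limits for these versions. If the 11.0 floor seen in both the Version 4 and Version 7 criteria applied, the overlap would be 11.0-11.4 and 11.0-12.4.

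**5. What the margins allow.** With n subjects in an arm, b graded at baseline and d graded at Day 7, the number newly graded lies between max(0, d − b) and min(d, n − b). The asymptomatic population is 34 subjects in four disease-by-arm cells, 34/4 = 8.5 each if even. For illustration, take n = 9, b = 3, d = 3. The lower bound is max(0, 0) = 0 and the upper bound is min(3, 6) = 3, so the table is compatible with no new case or with three. One carried-over subject is 1/9 = 11.1 or 1/8 = 12.5 points of an arm. With b = 0 the two bounds coincide at d, which is the Version 7 case.

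**6. Baseline rows in Tables 51-58.** SAP section 9.6 takes baseline laboratory values at screening, before dosing. A result at that time cannot be related to treatment, so these rows can hold only zeros or errors.

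**The case against.** The best reply is that the information is already planned. Baseline stands beside Day 7 for each arm, Tables 59-66 summarize change, Tables 44-45 list each abnormal result by subject and time point, Listings 25-30 give every value, and Figures 22-23 plot both times. With eight or nine subjects in an arm, a reader could work out who worsened. Randomization balances carried-over grades in expectation, and no test or halting rule uses these tables. Most of this stands, and it keeps the point minor. What it does not supply is a by-arm count of worsened grades: a mean or median change can hide one subject crossing a threshold, and a listing leaves the count to the reader.

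Four stronger readings are tempting, and the documents do not support them.

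- A reader might infer that Table 48 as printed merges directions. It does not. It is the asymptomatic table, those subjects enrolled under Versions 1-4, and high hemoglobin has no grade before Version 7.
- A reader might infer that the tables cannot show treatment-emergent toxicity. That is too strong, given the listings and change summaries and the absence of overlap under Version 7.
- A reader might infer a conflict with Protocol section 9.2.1, which says that "if the severity of any pre-existing medical condition increases, it will be recorded as an AE". That sentence concerns medical conditions. For laboratory values, Protocol section 9.2.3 uses absolute thresholds and section 6.3 has any Day 7 abnormality evaluated as an adverse event.
- A reader might infer that liver toxicity is obscured. No severity shell is listed for AST, ALT, BUN or creatinine; they can enter only through the any-parameter Table 46.

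**Conclusion.** The point holds as a minor improvement to the safety displays. Efficacy endpoints are untouched.

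The hemoglobin merge is certain from the layout for Version 7 samples in the symptomatic repeats of Tables 48, 52 and 56. How often it will occur is unknown, since an eligible subject must rise above 18.0 by Day 7. Each occurrence is worth 2.9 points in a full arm.

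Carry-over is shown only for the asymptomatic Version 4 subjects, at 11 to 13 points per subject. That size assumes an even split of the 34, and the overlap assumes that the wider eligibility list governed entry. It does not arise under Version 7. For Versions 5-6 it is possible for hemoglobin only, and only if the unstated entry floor was 11.0.

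**What to change.** - Give the symptomatic repeats of Tables 48, 52 and 56 the Low/High columns already used for white cells and platelets.
- Add to Tables 46-50 and their repeats a row counting subjects whose Day 7 grade is worse than baseline in the same direction, or add a shift table. Apply it to graded parameters only; hematocrit (Table 49) has no grade in SAP Table 7.
- For that row, grade both samples under one protocol version and name it in a footnote. Otherwise a change of version between the two dates alters the grade of an unchanged value: platelets of 140 are Grade 1 under Version 4 and ungraded under Version 5.
- Delete the Baseline rows from Tables 51-58.

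The cost is shell edits and minor programming. No new data are needed.
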